10.2 Processing

All skin biopsy specimens will be sent and processed at the University of Arizona Cancer Center in Tucson, in [name] laboratory..Karyometry analysis will be done at [name] laboratory for all specimens. Karyometric measures of nuclear abnormalities scores will be recorded for statistical analysis.

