10. PHARMACOKINETIC STUDIES

10.1 Collection

One skin biopsy with a 4-mm punch will be taken from each forearm (treatment and non treatment sites) prior to the first session and another skin biopsy with a 4-mm punch will be taken at the end of all the sessions at 3 years, on each forearm of all patients for a total of 4 biopsies per patient. Gelfoam or 1-2 sutures will be used to close the biopsy site.

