10.3 Storage

Specimens and slides will be kept in a slide portfolio, properly labelled and stored in [name] lab.

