16. STATISTICAL CONSIDERATIONS

Characteristics of study subjects will be summarized by appropriate abstract statistics, including frequency, proportion and 95% Clopper-Pearson confidence interval (CI) for the proportion for categorical variables, median, and range for continuous variables.

Evaluable subjects for safety outcome measures will be those who complete any study visits or those who discontinue the study treatments due to adverse events (AE).
Evaluable subjects for efficacy outcome measures will be those who complete all study visits. At least 15-16 evaluable subjects for each of these analyses are expected.

Primary efficacy outcome measure will be the difference in the total number of AK/NMSC in the treatment areas compared to the control areas. All unique AK/NMSC

observed during the 3 year study period will be identified and summed in each area. The statistical significance of the difference will be tested using the Wilcoxon Signed-Rank Test.

Secondary safety and efficacy measure: Time to the occurrence of the first AK/NMSC in the control versus treated areas will be estimated using the Kaplan-Meier estimate. Changes in the p53 staining from baseline to end of treatment will be evaluated using McNemar's Test. Mean pain scores (VAS) and photo damage scale global scores of the study population will be compared with each respectively using Wilcoxon Signed-Rank Test.

Sample Size Determination: Safety will be evaluated using a one-sided confidence interval (as the lower bound is not of interest). At least fourteen patients will be evaluable for safety. If none of the patients have an adverse primary safety outcome, the upper bound of a 95% one-sided confidence interval is < 20%.

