17.2 Efficacy Analysis

Number of AK/NMSC will be counted for each site using the photographs of the treatment and the control areas. AKs will be graded by thickness I-III: I = mild, slightly palpable, II = moderate, easily felt, III= severe, very thick. NMSC, including basal cell carcinoma, Bowen's disease and squamous cell carcinoma, will be diagnosis and confirmed histologically by biopsy.

Photo damage in the treatment and control fields will be assessed by the sun damage scale as: absent, mild, moderate, and severe. The scale includes 4 points: fine wrinkling, coarse wrinkling, abnormal pigmentation and global (0-10). Ratings for epidermal dysplasia will be obtained by immunohistochemistry of p53 staining of skin biopsies in the treatment areas at baseline and after the last treatment.

Time to occurrence of AK/NMSC will be calculated from the first visit to the development of an AK or NMSC in the treatment areas and in the control areas.

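### p53 is tested only as a before-after change on the treated side over 3 years, and the plan states neither single-run staining nor a masked reader

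*Combined protocol and SAP*

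**What the plan says.** **Collection.** Section 10.1 takes one punch biopsy from each forearm, treated and untreated, before the first session. Then "another skin biopsy with a 4-mm punch will be taken at the end of all the sessions at 3 years". This second sampling again covers both sides, which makes four specimens for every subject.

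**Processing and storage.** Section 10.2: "All skin biopsy specimens will be sent and processed at the University of Arizona Cancer Center in Tucson". Karyometry is done in one "laboratory for all specimens. Karyometric measures of nuclear abnormalities scores will be recorded for statistical analysis". Section 10.3: "Specimens and slides will be kept in a slide portfolio, properly labelled and stored in" a named laboratory. None of these sections says when tissue is stained or read, whether a subject's specimens share a run, or whether slides are coded. The rest of the protocol does not supply this either.

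**p53.** Section 17.2 obtains the dysplasia ratings by "immunohistochemistry of p53 staining of skin biopsies in the treatment areas at baseline and after the last treatment". Section 16: "Changes in the p53 staining from baseline to end of treatment will be evaluated using McNemar's Test". No positivity cut-off, significance level or control-side term is given.

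**Karyometry.** By contrast, the endpoint list in Section 1.3 names karyometric change in both the treated and the untreated fields. p53 is not in that list, and schedule footnote F (Section 26) gives karyometry as the use of the biopsies.

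**The concern.** The p53 test has no concurrent control. It sets slides from before PDT against slides from about 3 years later on the same forearm and attributes the difference to treatment. Two other things can differ between those slides.

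- **The laboratory.** If the time points are processed in separate runs, a lasting change of antibody lot, instrument or reader produces the same discordant pairs as a treatment effect.
- **The skin.** Three further years of immunosuppression and sun exposure may change p53 without PDT.

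The error could go either way. A spurious fall would look like confirmation of the rationale, because Section 4.4 cites reduced expression of early carcinogenesis markers, p53 among them, after repeated PDT. A spurious rise could hide a real effect.

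Masking is a separate gap. A reader who knows side and visit can shift p53 ratings and karyometric scores alike, and having both forearms does not protect karyometry from that.

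**Working it through.** **The plan's own figure.** There is none for p53 or karyometry. The only sample-size figure, in Section 16, is for safety: 0 events in 14 gives a one-sided 95% upper bound of 1 − 0.05^(1/14) = 19.3%, so the stated limit of under 20% reproduces. It has no bearing on this point.

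**Inputs.** Number of pairs: 15, the lower end of the 15-16 evaluable subjects in Section 16. Test: McNemar, Section 16. Assumed because the documents are silent: a positive/negative p53 rating, the exact two-sided form, a 5% level, and the size of any drift. No PDT effect is present in any row below.

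**Step 1: what the test needs.** Let b pairs go positive to negative and c go negative to positive. Then p = min(1, 2 × P[X ≤ min(b, c)]), X ~ Bin(b + c, 0.5). Five discordant pairs in one direction give 2 × 0.5^5 = 0.0625. Six give 2 × 0.5^6 = 0.031. So at least six are needed.

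**Step 2: rejection under drift alone.** The result depends on how the two ratings of a subject are linked, so three models are shown.

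- *Independent ratings*, positive rate moving from p0 to p1: P(+ to −) = p0(1 − p1) and P(− to +) = (1 − p0)p1. For 60% to 40% these are 0.6 × 0.6 = 0.36 and 0.4 × 0.4 = 0.16.
- *Drift in one direction only*: P(+ to −) equals the shift and P(− to +) = 0. Rejection is P[Bin(15, shift) ≥ 6].
- *Mixed*: P(− to +) = 0.10 and P(+ to −) = 0.10 plus the shift.

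Summing the exact multinomial probabilities over all (b, c) with p ≤ 0.05:

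| Assumed shift | Independent (rates used) | One direction | Mixed |
|---|---|---|---|
| none | 1.8% (60/60) | 0% | 0.2% |
| 10 points | 3.5% (60/50) | 0.2% | 2.1% |
| 20 points | 9.7% (60/40) | 6.1% | 9.9% |
| 30 points | 22.7% (70/40) | 27.8% | 23.8% |

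**Step 3: the same drift with the control forearm used.** Score each forearm's change as −1, 0 or +1 and take treated minus control. If both forearms drift alike, positive and negative differences are equally likely, and an exact sign test keeps its level. Example, 60% to 40% with independent ratings: the changes −1, 0, +1 have probabilities 0.36, 0.48, 0.16. The chance of a negative difference is 0.36 × 0.48 + 0.36 × 0.16 + 0.48 × 0.16 = 0.307, and that of a positive one is the same. The test rejects in 2.2% of trials. With changes taken as independent between forearms, no drift row in the table exceeds 2.2%.

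**Step 4: what each remedy removes.**

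| Source of difference | One run per subject | Change compared between forearms | Coded slides |
|---|---|---|---|
| Reagent or instrument drift | yes | yes, if common to both sides | no |
| Natural change over 3 years | no | yes, if common to both sides | no |
| Ageing of stored baseline tissue | no | yes, if common to both sides | no |
| Reader's knowledge of side or visit | no | no | yes |

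**The case against.** **Silence is not a statement.** A reader might infer that baseline tissue is read on arrival, so that laboratory drift is built into the p53 comparison. The documents do not say so. Sections 10.2 and 10.3 give a place of processing, one karyometry laboratory for all specimens, and storage of specimens and slides. A single run at the end fits that text as well. This stands, and the laboratory part of the point is conditional on separate runs.

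**Staggered entry breaks up the alignment.** The 16 to 20 subjects in Section 2.3 need not enter together. If tissue were processed as received, baseline slides could be spread over many runs. Random run-to-run variation would then mostly add noise. Only a sustained trend, or a step between the two periods, would line up with before versus after. This also stands.

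**The size is assumed.** A 10-point shift leaves the false-positive rate below 5% under all three pairing models, because the exact test is conservative at this size. A material excess needs 20 to 30 points, and the documents offer no basis for or against that. This stands.

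**Limited consequence.** This is a pilot, p53 is a secondary measure, and it is missing from the endpoint list. Karyometry covers both fields, so drift common to the two forearms cancels when they are compared. That stands too, except that it does not cover an unmasked reader.

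**What none of this answers.** The p53 comparison remains treated-side only across 3 years. Even perfect single-run staining would not separate PDT from natural change.

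**Conclusion.** The point holds as a gap in specification plus an uncontrolled comparison. The plan does not require single-run processing or masked reading, and its p53 test uses no control-side value although the control tissue is collected at both times. If the time points are run separately and the laboratory shifts in a lasting way, the planned test cannot distinguish that from a PDT effect. Natural change over 3 years is confounded with PDT regardless of how the slides are run.

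Its size cannot be derived from the documents. With 15 pairs, an exact two-sided 5% McNemar test and assumed shifts of 10 to 30 points, false-positive rates run from 0.2% to 27.8%. They depend on both the shift and the correlation between a subject's two ratings.

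Two stronger readings are not supported. One is that drift is certain to be aligned with time point, which would need a statement on timing that the protocol does not make. The other is that the trial's main result is compromised: the primary AK/NMSC count does not use the biopsies. This is a low-cost improvement to a secondary measure.

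**What to change.** **Section 10.2, add:** Blocks will be held until the subject's final biopsy is received, or until the subject leaves the study without one. All specimens of a subject will be cut, stained for p53 and measured by karyometry in the same run. Slides will carry a code that hides side and time point from the reader until ratings are locked.

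The second condition in the hold rule is needed because the schedule in Section 26 has no biopsy at early termination.

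**Sections 17.2 and 16, change:** Rate p53 on the control-forearm biopsies as well, and compare the baseline-to-end change between forearms within subject. State the rating scale or positivity cut-off and the test; for a positive/negative rating, an exact sign test on the difference in change would serve. Add p53 to schedule footnote F so that the uses of the tissue agree.

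**Timing.** The coding and holding rule has to be in place before any baseline slide is read, because an unmasked early reading cannot be undone.

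**Cost.** No biomarker result before a subject's third year. p53 staining of two further existing specimens per subject, at most 2 × 16 = 32 to 2 × 20 = 40 in all. No new patient procedure, the same laboratory, and storage is already planned in Section 10.3.

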10.3 Storage

Specimens and slides will be kept in a slide portfolio, properly labelled and stored in [name] lab.

10.4 Destruction

Not Applicable

11. DATA AND SAFETY MONITORING PLAN

Data and Safety Monitoring Plan: Medium

Medium risk studies are intended to include all trials involving therapeutic intervention(s), which are **not** designated as high risk per NCI, do not meet the criteria of medium plus IND risk, and **do not require an IND (i.e. IND exempt)**.

11.1 Identification of the DSMB obligated for oversight responsibilities

The Arizona Cancer Center Data and Safety Monitoring Board (DSMB) will provide ongoing oversight for this trial.

11.2 Identification of the entity obligated for routine monitoring duties

Routine monitoring will be provided by the Quality Assurance/Quality Control (QA/QC) Program to ensure that the investigation is conducted according to protocol design and regulatory requirements. All processes, subject information and study data will be recorded in the study regulatory binder(s) and in OnCore, which will be available to the monitoring staff.

11.3 Monitoring progress and data review process

Routine monitoring of subject data will be conducted at least annually.

The first routine monitoring visit will include at a minimum:

- Informed consent – 100% of cases enrolled;
- Subject eligibility - 50% of cases, up to two subjects;
- Data review - 50% of cases, up to two subjects.

All subsequent monitoring visits will consist of randomly selected subject cases based on current enrollment and include continuing review of previously selected cases, as applicable.

A monitoring visit report and follow-up letter will be completed-approximately two weeks after the routine monitoring visit; a copy will be maintained in the study file. A query/finding form or an electronic record will also be completed by the monitor to request additional source documentation, clarification, information or corrections to the CRF and/or regulatory records. The Clinical Research Coordinator or other applicable staff responsible for the study will be given a copy of this form, or will be notified of the electronic record for resolution of queries/findings. The query/finding form will be maintained with a copy of the visit report for follow-up at the next monitoring visit. Electronic records will be available in the institution database or provided by the QA/QC Program staff.

The Principal Investigator will ensure the accuracy, completeness, legibility and timeliness of the data reported in the Case Report Form (CRF). Source documentation supporting the study data should indicate the subject's participation in the trial and should document the dates and details of study procedures, adverse events, and patient status.

Case report forms, which include the inclusion/exclusion criteria form, adverse event forms and serious adverse event forms [*other forms, depending on study*] will be completed via the institution database. All subject forms and study files will be stored in a secure area limited to authorized staff.

11.4 Process to implement study closure when significant risks or benefits are identified

The PI will be advised of all study related AEs and will determine if the study should be closed due to significant AEs and risks.

11.5 Description of adverse events and reporting procedures

ADVERSE EVENTS: An adverse event (AE) is any untoward medical occurrence in a patient or clinical investigation subject administered a pharmaceutical product and that does not necessarily have a causal relationship with this treatment. An AE can therefore be any unfavorable and unintended sign, symptom, or disease temporally associated with the use of a medicinal (investigational) product, whether or not related to the medicinal (investigational) product.

Any and all adverse events will be recorded on the UACC adverse events record form and reviewed by the Principal Investigator.

All adverse events will be classified using either the MedDRA term or NCI Common CTCAE version 4.02 and will address:

- Grade
- Relationship to study drug (not related, unlikely, possible, probable, definitely)
- Causality other than study drug (disease related, concomitant medication related, intercurrent illness, other)
- Date of onset, date of resolution
- Frequency of event (single, intermittent, continuous)
- Event outcome (resolved, ongoing, death)
- Action taken (none, held, dose reduced, discontinued, medication given)

SERIOUS ADVERSE EVENTS: An SAE is any untoward medical occurrence that at any dose:

- 1) Results in death;
- 2) Is life-threatening;
- 3) Requires in-patient hospitalization or prolongation of an existing hospital stay;
- 4) Results in disability persistent or significant disability/incapacity, or;
- 5) Is a congenital anomaly/birth defect.

Note: A SAE may also be an important medical event, in the view of the investigator that requires medical or surgical intervention to prevent one of the outcomes listed above.

All serious adverse events, regardless of attribution, and any deaths will be reported within 24 hours of notification of the event to the sponsor and DSMB Coordinator. All serious adverse events, regardless of attribution, and any deaths will be reported within 5 days of notification of the event to the University of Arizona Human Subjects Protection Program.

All serious adverse events will be processed by the DSMB Coordinator monthly for initial trend analysis and fully reviewed by the DSMB every six months. The DSMB coordinator will review the SAE reporting process to confirm reporting requirements are met.

11.6 Plan for assuring data accuracy and protocol compliance

Routine study activity and safety information will be reported to the DSMB every six months, or more frequently if requested. These reports will include:

- Study activity, cumulative and for the period under review;
- Safety (narrative description on non-serious and serious adverse events, protocol pre-determined early stopping rules for safety or treatment-emergent adverse events);
- Predetermined protocol early stopping rules for efficacy/futility;
- Status of study in relationship to stopping rules;
- Current dose level of study agent;
- Routine monitoring and protocol compliance (describe the monitoring process and identify the status of the monitoring);
- Comments;
- Attachments (AE data reviewed by the PI to compile the report, SAE letters and reports, results of any review(s), applicable correspondence with the IRB or other regulatory agencies.

Data, safety and study progress will be reported to:

- Human Subjects Protection Program (IRB) at least annually;
- Sponsor (if applicable) at least every six months.

11.7 Identification of the sponsor or funding agency, as applicable

The PI will immediately notify; in writing, the funding agency, if applicable, any action resulting in a temporary or permanent suspension of the study. A copy of this correspondence will also be forwarded to the DSMB and the SRC.

12. ADDITIONAL SAFETY REPORTING REQUIREMENTS

Not Applicable.

13. QUALITY ASSURANCE MEASURES

Per the UACC DSMB Charter, Internal *Ad Hoc* audits may be performed on any UACC clinical trial if identified for audit, the audit will be conducted by an identified audit team per the UACC DSMB Charter. A QA/QC representative will coordinate the audit team functions and a written audit report will be provided to the principal investigator and the DSMB.

14. RECIST CRITERIA

Not Applicable.

15. REMOVAL OF SUBJECTS

Subjects have the right to withdraw from the study at any time and for any reason without prejudice to their future medical care by the physician or at the institution. If this occurs, the investigator, or designee, is to discuss with the subject the safe and appropriate processes for discontinuation from the investigational treatment.

The investigator or designee must document the change in status of the subject's participation in the study and as applicable, the level of follow up that is agreed to by the subject (i.e. agrees to follow up exams, adverse event review, but not to further treatment and/or procedures).

Subject withdrawal of consent for a study indicates that the subject does not wish to receive further protocol required therapies or procedures, and the subject does not wish to, or is unable to continue further study participation. Subject data only up to the time when consent is withdrawn will be included in the analysis of the study.

The study is expected to close after all patients have been treated for 3 years.

16. STATISTICAL CONSIDERATIONS

Characteristics of study subjects will be summarized by appropriate abstract statistics, including frequency, proportion and 95% Clopper-Pearson confidence interval (CI) for the proportion for categorical variables, median, and range for continuous variables.

Evaluable subjects for safety outcome measures will be those who complete any study visits or those who discontinue the study treatments due to adverse events (AE).
Evaluable subjects for efficacy outcome measures will be those who complete all study visits. At least 15-16 evaluable subjects for each of these analyses are expected.

Primary efficacy outcome measure will be the difference in the total number of AK/NMSC in the treatment areas compared to the control areas. All unique AK/NMSC

observed during the 3 year study period will be identified and summed in each area. The statistical significance of the difference will be tested using the Wilcoxon Signed-Rank Test.

Secondary safety and efficacy measure: Time to the occurrence of the first AK/NMSC in the control versus treated areas will be estimated using the Kaplan-Meier estimate. Changes in the p53 staining from baseline to end of treatment will be evaluated using McNemar's Test. Mean pain scores (VAS) and photo damage scale global scores of the study population will be compared with each respectively using Wilcoxon Signed-Rank Test.

Sample Size Determination: Safety will be evaluated using a one-sided confidence interval (as the lower bound is not of interest). At least fourteen patients will be evaluable for safety. If none of the patients have an adverse primary safety outcome, the upper bound of a 95% one-sided confidence interval is < 20%.

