17. ANALYSIS

17.1 Safety Analysis

The primary safety outcome measures will be estimated with 95% Clopper-Pearson CI: The proportion of evaluable study participants who had a grade 3 or higher AE or any serious adverse event that's determined to be at least possibly or probably related to study treatment, or any AE which is at least possibly or probably related to study treatment that causes permanent study discontinuation. AE's will be documented and kept in the study regulatory binder and in OnCore.

Pain will be assessed on the 10 point Visual Analogue Scale (VAS), as mild (0-3), moderate (4-7) or severe (8-10). Patients will be asked to rate the pain at the beginning, midway point (approximately 8 minutes later), and at the end of each PDT session.

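### As worded, the safety-evaluable set can include registered subjects who completed only the screening visit and were never treated (minor; one-sentence fix)

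*Combined protocol and SAP*

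**What the plan says.** Section 16 defines the safety set in one sentence with two routes in. The first is: "Evaluable subjects for safety outcome measures will be those who complete any study visits". The second adds subjects who stop study treatment because of an adverse event. Neither route mentions having received treatment.

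The efficacy set is stricter: "Evaluable subjects for efficacy outcome measures will be those who complete all study visits". On numbers, section 16 says "At least 15-16 evaluable subjects for each of these analyses are expected". Its sample size paragraph then says "At least fourteen patients will be evaluable for safety" and, for the case of no events, "the upper bound of a 95% one-sided confidence interval is < 20" percent.

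Section 17.1 puts this set in the denominator of the primary safety outcome, which begins: "The proportion of evaluable study participants who had a grade 3 or higher AE or any serious adverse event". It goes on to refer to relatedness to study treatment and to related events that cause permanent discontinuation.

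Three other places bear on who can be in the set:
- Section 26 (schedule): Screening/Baseline is Visit 1. Levulan-PDT and adverse event recording both start at Visit 2 (Day 1). Screening may take place up to 28 days before first treatment.
- Section 9.4: the last PDT is at visit 9. This agrees with the schedule, in which Visits 2 to 9 are the eight treatments.
- Section 6.3: every subject who completes screening is registered and given a study number.

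**The concern.** Screening is a numbered study visit, and registration follows it. A subject can therefore be registered, have completed a visit, and leave during the interval of up to 28 days before Day 1. On the wording of section 16 that subject is evaluable for safety.

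Such a subject adds one to the denominator of the 17.1 proportion and cannot add a treatment-related event. Any bias runs one way. The proportion (when events occur) and its upper bound come out lower, with no added information about Levulan-PDT. Safety is part of the primary objective in section 3.1, and the safety bound is the only basis given for the sample size, so the denominator should be stated exactly.

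**Working it through.** **Inputs.** Section 16: 95% one-sided interval, minimum of 14 evaluable, zero-event bound below 20%, 15-16 evaluable expected. Section 2.3: 16 to 20 enrolled. The number registered but never treated is not in the documents, so I take k = 0 to 3 as an assumption.

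**Step 1: reproduce the plan's figure.** With zero events in n subjects, the exact one-sided 95% upper bound is 1 − 0.05^(1/n).
- n = 14: 1 − 0.05^(1/14) = 19.26%, which is below 20%.
- n = 13: 1 − 0.05^(1/13) = 20.58%, which is not.

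The stated figure is correct, and 14 is the smallest number that meets it. There is no slack at the floor.

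**Step 2: separate counted from treated.** If N subjects are counted and k of them were never treated, the reported bound uses n = N, while the treated subjects support only the bound at n = N − k. With zero events:

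| Counted (N) | Reported (same as k = 0) | Supported, k = 1 | k = 2 | k = 3 |
|---|---|---|---|---|
| 14 (floor) | 19.3% | 20.6% | 22.1% | 23.8% |
| 15 (expected) | 18.1% | 19.3% | 20.6% | 22.1% |
| 16 (expected) | 17.1% | 18.1% | 19.3% | 20.6% |

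The bound for treated subjects is below 20% whenever N − k is at least 14. That allows no untreated subjects at 14 counted, one at 15 and two at 16.

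**Step 3: one event.** The exact one-sided upper bound is the 0.95 quantile of a beta distribution with parameters (2, n − 1). With 16 counted and one untreated:
- as worded (n = 16): 1/16 = 6.3%, upper bound 26.4%;
- treated only (n = 15): 1/15 = 6.7%, upper bound 27.9%.

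**Step 4: what the plan itself expects.** Section 16 expects 15-16 subjects in each analysis set, including the efficacy set, whose members complete every visit. All of those are treated. The zero-event bound for treated subjects is then at most 18.1% (15 completers) or 17.1% (16), however many untreated subjects are also counted.

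**The case against.** The strongest reply is that treated subjects were plainly meant. If screening counts as a qualifying visit, the adverse-event route adds nobody, because anyone who stops treatment has already completed screening. If visits means treatment visits, that route has a purpose: it catches a subject who stops for an adverse event before completing Day 1. The schedule also separates Screening/Baseline from the on-treatment columns, and section 11.5 defines an adverse event in a subject who has been given a product.

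This stands as evidence of intent, but it does not settle the rule. Section 11.5 does not define a denominator. The treatment-visit reading also has a gap of its own: a subject treated on Day 1 who leaves before finishing that visit, for a reason other than an adverse event, would be excluded despite exposure. Neither reading gives exactly the exposed subjects.

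It is also fair to say that the subject log in section 6 records on-treatment dates, so untreated registrants can be identified and a treated-only proportion computed. That makes any dilution visible and reversible. It does not say which denominator is primary.

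A reader might go further in two ways that the documents do not support:
- Section 15 says "Subject data only up to the time when consent is withdrawn will be included in the analysis of the study". This limits which data are used. It does not place withdrawn subjects in the safety set, and the point does not need it.
- The grammar of 17.1 leaves open whether relatedness also qualifies grade 3 or higher events, so one might think an untreated subject could add an unrelated event. Under the section 11.5 definition, and with no adverse event recording at Visit 1, that is doubtful.

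**Conclusion.** The wording of section 16 admits never-treated registrants to the primary safety denominator, and no section limits the set to treated subjects. That much is certain from the text. The size is conditional on a number the documents do not give:
- if all registered subjects are treated, there is no effect;
- if one is not, the zero-event bound is understated by about 1.3 percentage points at the floor of 14 (19.26% against 20.58%) and about 1.0 point at 16 counted (17.07% against 18.10%).

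A reader might infer that untreated subjects will in fact be counted, or that the plan's statement about 20% is wrong. Neither follows. Intent probably runs the other way, the arithmetic at 14 is correct, and with the expected 15-16 completers the statement holds for treated subjects. The 20% figure describes precision; no stopping or success rule depends on it. Severity: minor.

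**What to change.** In section 16, define safety-evaluable subjects as all subjects who received at least one Levulan application, that is, any part of a Levulan-PDT treatment. Application is the right trigger because sections 7.1 and 8.1 describe illumination only after it. Apply the minimum of fourteen to that set. Report subjects who were registered but not treated in the disposition only.

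The cost is a short wording change and no new data. The downside is that the evaluable number may be slightly smaller and the bound slightly less favourable.
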